### Sample size considerations

The primary endpoint in this power analysis is the Zarit's caregiving burden score. Assuming 20% attrition rate at the 6-month follow-up, we plan to initially enroll totally 240 family caregivers who will be equally randomized into two will be equally randomized into two arms (120 per arm), and we expect a minimum of 100 caregivers per arm to complete the 6-month assessment. The sample size of 100 in each arm can guarantee 80% power at significance level 0.05 to detect the effect size of 0.28 standard deviation (SD)

difference between baseline and 6 months follow-up in a two-sided paired t-test. (See Table 4). Nicholas et al. reported the effect size of 0.33SD of Zarit's score from the REACH VA intervention (also between baseline and 6-month follow-up). While GP4C will use a different delivery strategy than used in the REACH II and REACH VA trials, core therapeutic materials and techniques of the intervention are maintained. Thus, we expect GP4C to have a similar impact on caregiver outcomes as observed in prior REACH II trial. Thus, we conclude that enrolling 120 caregivers per arm (100 available at 6 months) will achieve sufficient statistical power to detect the effectiveness of the proposed interventions, even if the GP4C full functionality intervention is slightly less robust than the original REACH interventions.

*Table 4. Sample size and power by effect size*

Effect size of 0.28 standard deviation (SD) difference		Effect size of 0.33 standard deviation (SD) difference	
Sample Size	Power	Sample Size	Power
70	.646	70	.777
80	.706	80	.830
90	.757	90	.872
100	.800	100	.905
110	.834	110	.929
120	.868	120	.948
130	.893	130	.962
140	.914	140	.972
150	.931	150	.980

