**Two specific staged AIMS are proposed in this study.**

**AIM 1. Advance the current proof-of-concept GP4C into a viable delivery system for the REACH II intervention.** Further development will include uploading the full breadth of REACH II education and skill-building materials, usability testing and updates to the user interface/user experience (UI/UX), creating a portal of delivery tools used by Dementia Care Specialist (DCS; i.e., interventionist), and establishing a comparable education-focused online system (Resources4Care; R4C) to be used in comparison to the multicomponent, skills-training GP4C system. Development activities will be conducted by the Baylor Scott & White Health (BSWH) Office of Digital Health with engagement of community-based organizations, family caregivers, and external advisors, with oversight by the GP4C research team.

**H1:** *Within 12 months of usability testing with 32 family caregivers, the GP4C research team will reach consensus with the BSWH Office of Digit Health and an external Advisory Committee that GP4C is a viable platform for online delivery of REACH II with R4C as an appropriate comparison condition.*

**AIM 2. Compare the relative impact of GP4C and R4C, both of which include access to a Dementia Care Specialist, on a wide range of family caregiver outcomes.** Family caregivers will be randomized to one of the two conditions and will complete an assessment battery at baseline and at the 6-month follow-up. Primary outcome measures will include burden, depression, social support, and caregiver's health and interaction with health care providers. Secondary outcomes will include caregiver stress, positive aspects of caregiving (PAC), cognitive change in care-recipient. The CBOs will designate a "GP4C Champion" to promote the enrollment of 240 family caregivers who have computer access and report regular use of the internet. Use of GP4C & R4C and contact with DCS will be recorded by the system as implementation data.

**H1:** *Family caregivers randomized to the GP4C condition will report greater improvement on primary and secondary outcomes as compared to family caregivers in the R4C condition.*

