### 4.3 Sample Size Considerations

The primary endpoint in this power analysis is the Zarit's caregiving burden score. Assuming 20% attrition rate at the 6-month follow-up, we plan to initially enroll totally 240 family caregivers who will be equally randomized into two will be equally randomized into two arms (120 per arm), and we expect a minimum of 100 caregivers per arm to complete the 6-month assessment. The sample size of 100 in each arm can guarantee 80% power at significance level 0.05 to detect the effect size of 0.28 standard deviation (SD) difference between baseline and 6 months follow-up in a two-sided paired t-test. (See Table 4). Nicholas et al. reported the effect size of 0.33SD of Zarit's score from the REACH VA intervention (also between baseline and 6-month follow-up). While GP4C will use a different delivery strategy than used in the REACH II and REACH VA trials, core therapeutic materials and techniques of the intervention are maintained. Thus, we expect GP4C to have a similar impact on caregiver outcomes as observed in prior REACH II trial. Thus, we conclude that enrolling 120 caregivers per arm (100 available at 6 months) will achieve sufficient statistical power to detect the effectiveness of the proposed interventions, even if the GP4C full functionality intervention is slightly less robust than the original REACH interventions.

*Table 4. Sample size and power by effect size*

| Effect size of 0.28 standard deviation (SD) difference |       | Effect size of 0.33 standard deviation (SD) difference |       |
|--|-------|--|-------|
| Sample Size  | Power | Sample Size  | Power |
| 70   | .646  | 70   | .777  |
| 80   | .706  | 80   | .830  |
| 90   | .757  | 90   | .872  |
| 100  | .800  | 100  | .905  |
| 110  | .834  | 110  | .929  |
| 120  | .868  | 120  | .948  |
| 130  | .893  | 130  | .962  |
| 140  | .914  | 140  | .972  |
| 150  | .931  | 150  | .980  |

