## 6 Statistical Methods and Analyses

Caregiver participants will be randomized to the two intervention arms (GP4C and R4C) with the ratio of 1:1. Primary and secondary outcomes, including the Zarit's caregiving burden interview, will be assessed at baseline and 6-month follow-up. Covariates in the analysis include demographic characteristics of the caregivers. Common descriptive statistics (mean, standard deviation, median, interquartile range for continuous variable; frequency and percentage for categorical variables) will be calculated for all covariates in each intervention arm and the two arms will be compared at baseline. Goals of our statistical analysis will be to evaluate the effectiveness of each intervention arm and to compare the two arms. For each intervention arm, the difference between 6-month follow-up and baseline will be computed. Paired t-test and Wilcoxon signed-rank test will be used to detect significant changes in outcome variables at 6-month follow-up since the baseline. Medians, means, and 95% confidence intervals of the differences will be calculated using both empirical percentiles and normal approximation. Multiple comparison adjustments, e.g., Holm-Bonferroni method and Hochberg procedure, will be implemented to control the family wise error rate when testing multiple outcome measures in Section 5.

The two intervention arms will be compared at each follow-up time and for the whole trial period. We will compare the two arms at 6-month follow-up using the two-sample t-test and Wilcoxon rank sum test for each of the two outcomes. The Anderson-Darling test will be used to check the normality assumption at baseline and follow-up times for the two outcome variables. If normal assumption is significantly violated then only nonparametric estimates and tests (i.e., median, IQR, empirical confidence intervals, Wilcoxon signed-rank test, and Wilcoxon rank sum test) will be reported, and data transformation, such as log and square root transformations, will be considered to normalize the outcome variables for further model-based testing. A pre-post analysis will be conducted to model the outcomes at 6-month follow-up to test the intervention arm and covariates adjusting the baseline measurements. The two arms will also be compared incorporating observations from baseline and follow-up in longitudinal analysis of covariance (ANCOVA) models or linear mixed-effects models having the follow-up time and adjusting for covariates.

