Given the fact that participants will be randomized into the two arms, the outcome variables will likely be comparable between the two arms at baseline. As a result, the interaction effect between the treatment arm and follow-up time (while adjusting for covariates) will be tested in the longitudinal analysis to evaluate the difference between the two intervention arms because a significant interaction indicates the caregiver's outcome has followed significantly different trajectories in the follow-up period depending on the treatment arm. Missing values may be possible because 1) some caregivers may be lost to follow-up, and 2) some caregiving recipients can be deceased prior to the follow-up. Missing patterns will be inspected and multiple imputation methods, including regression imputation, propensity score imputation, and MCMC imputation will be considered based on the missing mechanism^19. All tests will be two-sided and a p-value less than or equal to 0.05 will be reported as statistically significant. Statistical Analysis Software will be used to conduct the proposed analysis.

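### The 80% power in SAP 4.3 is for change within one arm; for GP4C against R4C, 100 per arm gives about 50% power at the same 0.28 SD

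*SAP*

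**What the plan says.** SAP 4.3 names the endpoint: "The primary endpoint in this power analysis is the Zarit's caregiving burden score". It then states "The sample size of 100 in each arm can guarantee 80% power at significance level 0.05" to detect an "effect size of 0.28 standard deviation (SD) difference between baseline and 6 months follow-up in a two-sided paired t-test". The protocol's section on sample size considerations carries the same calculation, for a "difference between baseline and 6 months follow-up in a two-sided paired t-test". Table 4 gives power at sample sizes 70 to 150 for 0.28 and 0.33 SD. The 0.33 benchmark, from an earlier REACH VA study, is also described as a change from baseline to 6 months. Both documents conclude that power is sufficient.

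The Aim 2 hypothesis, in the Specific Aims of both documents, is comparative: GP4C caregivers "will report greater improvement on primary and secondary outcomes as compared to family caregivers in the R4C condition".

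SAP 6 sets two goals: "Goals of our statistical analysis will be to evaluate the effectiveness of each intervention arm and to compare the two arms". Paired t-tests and signed-rank tests examine change within each arm. Two-sample tests at 6 months, a baseline-adjusted model and an arm-by-time interaction compare the arms. On the significance level it says: "All tests will be two-sided and a p-value less than or equal to 0.05 will be reported as statistically significant". No power is given for any between-arm analysis.

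**The concern.** The calculation that justifies the trial's size answers a different question from the one the trial randomizes to answer. A paired test asks whether one arm changed. The hypothesis asks whether two arms changed by different amounts. For the same standardized effect and the same number per arm, the between-arm estimate has twice the variance, so power is much lower. The 0.33 SD benchmark does not bridge the gap, because it is described as a pre-post change and not as a difference from a control.

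Two misreadings follow. A null between-arm result could be taken as absence of effect in a trial with 80% power. And the better-powered paired tests could be reported as showing that an arm works, since SAP 6 names effectiveness of each arm as a goal and offers paired tests for within-arm change. Pre-post change in one arm cannot be separated from time trend or regression to the mean.

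**Working it through.** **Inputs.** From SAP 4.3: 100 completers per arm, effects of 0.28 and 0.33 SD, significance level 0.05, 240 enrolled (120 per arm), 20% attrition. From SAP 6: two-sided tests, 1:1 allocation. Not in the documents, so assumed: the change in R4C, the correlation *r* between baseline and 6-month burden, and whether the SD is that of the change score or of the raw score. A paired t-test standardizes by the SD of change, so that unit is used first.

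**Step 1: reproduce the plan's figure.** Paired t-test, noncentral t, df = n − 1, noncentrality = d√n.
- d = 0.28, n = 100: noncentrality 0.28 × 10 = 2.80; power 79.2% (80.0% by the normal approximation). Table 4 states .800.
- d = 0.33, n = 100: noncentrality 3.30; power 90.4%. Table 4 states .905.

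Over all nine rows, the 0.33 column agrees to within 0.001 and the 0.28 column to within 0.01. Table 4 is therefore one-arm power, and its sample size is the number in a single arm.

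**Step 2: the same effect between arms.** Two-sample t-test on change, df = 198, noncentrality = d√(n/2), R4C change zero.
- d = 0.28: 0.28 × √50 = 1.98; power 50.4%.
- d = 0.33: 0.33 × √50 = 2.33; power 64.1%.
- Difference detectable with 80% power: 0.398 SD.
- Completers per arm for 80% power: 202 at 0.28, 146 at 0.33. At 20% attrition the first means 202/0.8 = 252.5, so 253 per arm or 506 in total.
- With all 120 per arm analysed, power at 0.28 is 57.9%.

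**Step 3: effect of baseline adjustment, 100 per arm.** The SD of change is σ√(2(1 − r)) and the ANCOVA residual SD is σ√(1 − r²). An effect d in SDs of change becomes d√(2/(1 + r)). An effect d in raw SDs becomes d/√(1 − r²).

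| r | 0.28 SD of change | 0.28 raw SD | 0.33 SD of change | 0.33 raw SD |
|---|---|---|---|---|
| 0.3 | 69% | 54% | 82% | 68% |
| 0.5 | 62% | 62% | 76% | 76% |
| 0.7 | 57% | 79% | 71% | 90% |
| 0.8 | 55% | 91% | 69% | 97% |

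In raw-SD units, ANCOVA reaches 80% from r of about 0.71 (0.28) or 0.56 (0.33).

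If the two-sample test at 6 months is run on unadjusted 6-month scores, 0.28 SD of change becomes 0.28√(2(1 − r)) raw SD, and power is 64% at r = 0.3, 50% at 0.5 and 24% at 0.8.

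**Step 4: change in R4C.** With two-sample tests on change:
- R4C improves by 0.10 SD: net effects 0.18 and 0.23; power 24.5% and 36.7%.
- R4C worsens by 0.12 SD: net effect 0.28 + 0.12 = 0.40; power 80%.

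**Step 5: what separate paired tests can show.** Suppose both arms have the same true change of 0.20 SD. Each paired test has noncentrality 0.20 × 10 = 2.0 and power 50.8%. The chance that exactly one arm is significant is 2 × 0.508 × 0.492 = 50%, although the arms do not differ.

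**The case against.** The strongest reply is that nothing is miscalculated. The plan names the paired test openly, Table 4 is right for it, and within-arm evaluation is a declared goal of a study that the SAP calls Phase 1. That is true, and the fault is one of alignment rather than of computation. But this calculation is the only support for 240 participants and for the conclusion that power is sufficient, while the stated hypothesis is comparative.

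Second, the 50% is conditional. It needs the effect in SDs of change, an unadjusted comparison and no change in R4C. SAP 6 also plans baseline adjustment, and the plan expects 0.33, with 0.28 as a cushion. At 0.33, ANCOVA gives 82% to 69% in SDs of change as r goes from 0.3 to 0.8. This stands as a qualification: some combinations reach 80%. The documents do not say which one applies.

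Third, R4C might worsen, since the protocol's Significance section says that harm grows with time spent caregiving. That would enlarge the contrast. This also stands, so both directions are shown above. R4C is, however, an active comparator with educational content, two emails and two calls, so improvement cannot be ruled out.

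Fourth, SAP 6 does not say whether its 6-month two-sample test uses raw scores or change, and SAP 5 defines the outcome as change. The raw-score figures are therefore one reading and not the plan's declared analysis.

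Finally, 20% loss from 120 leaves 96 rather than 100, which moves the detectable difference to 0.406 SD and power at 0.28 to 48.8%. That slightly strengthens the point.

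**Conclusion.** The point holds, and the power statement is wrong as written for the trial's hypothesis. With 100 completers per arm and two-sided 0.05, the plan has 80% power for a between-arm difference of about 0.40 SD, not 0.28. At 0.28 SD of change with no change in R4C, an unadjusted comparison has about 50% power, and ANCOVA has 55% to 69% for r from 0.8 down to 0.3. ANCOVA reaches 80% at 0.28 only in raw-SD units with r of about 0.71 or more, unless R4C worsens. The unit, the correlation and the R4C change are assumptions because the documents state none of them. That the paired calculation does not address the comparison of arms needs no assumption.

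**What to change.** Keep the enrolment at 240. In SAP 4.3, Table 4 and the protocol's sample size section, replace the paired calculation with one for the between-arm comparison of burden. State the SD unit, the assumed baseline-to-6-month correlation and the assumed R4C change, with a range for each. Possible wording:

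> With 100 completers per arm and a two-sided 0.05 level, the trial has 80% power for a between-arm difference of 0.40 SD of change (two-sample comparison), or 0.40 × √(1 − r²) raw SD with baseline-adjusted ANCOVA. At 0.28 SD of change, with no change in R4C, the two-sample comparison has about 50% power.

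If 96 completers per arm are expected, as 20% attrition implies, use 0.41 SD. Also say how burden enters the Holm or Hochberg adjustment of SAP 6. If it shares 0.05 with the five primary outcomes, the first Holm step is at 0.01, where power for 0.40 SD is 59%.

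In SAP 6 and the protocol's Data Analysis section, label the paired t-test and signed-rank results as descriptive within-arm change with confidence intervals, and base every conclusion about effectiveness on the between-arm estimate.

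The cost is wording and one recomputed table. No participants are added, but the stated power becomes less favourable.

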## 5 Outcome Measures

### Change from Baseline Caregiving Burden at 6 months

A 12-item version of the Zarit Caregiver Burden Interview. The Zarit Caregiver Burden Interview (ZBI) is an assessment tool for evaluating caregiver burden. The ZBI consists of 12 items representing a statement related to some aspect of perceived burden. Respondents (i.e., caregivers) rate each item ranging 0 (=never) to 4 (=nearly always). Total ZBI score is the summation of 12 items ranging from 0 to 48. Higher scores indicate greater burden.

[Time Frame: Baseline and six months]

### Change from Baseline Depression at 6 months

#### Levels of depressed symptoms:

A 10-item version of the Center for Epidemiological Studies Depression (CESD) Scale is an assessment tool for evaluating depression. Each item represents a statement for which respondents indicate how often in the past week they have felt that way from 0 (= rarely or none of the time) to 3 (= most or almost all of the time). Total score is the summation of 10 items ranging from 0 to 30. Higher scores indicate higher levels of depressed symptoms.

[Time Frame: Baseline and six months]

### Change from Baseline Self-rated health at 6 months

#### Assessment of perception of general health status:

A single item of self-rated health assess caregiver's perception on his/her own health from 0 (=excellent) to 4 (=poor).

[Time Frame: Baseline and six months]

### Change from Baseline Social Support at 6 months

#### Assessment of availability of support and satisfaction with support from others:

Two constructs from Social Provision Scale (reliable alliance and guidance) are used to evaluate social support. Two constructs assess availability of support and satisfaction with support from others. Four items for each construct (total of 8 items) describe a statement for which respondents agree to what extent their relationships are with other people from 1 (= strongly disagree) to 4 (=strongly agree). A total score is the summation of 8 items ranging from 8 to 32. Higher scores indicate higher levels of social support.

[Time Frame: Baseline and six months]

Change from Baseline Interaction with Health Care Providers at 6 months

Assessment of the frequency and experiences of medical care management and coordination for care-recipients:

Nine items from the National Study of Caregiving (NSOC) ask about experiences and frequency of caregiver's interactions with care-recipients' health care providers. Each item represents a statement for which respondents indicate how often in the last 6 months they interacted with health care providers/workers.

[Time Frame: Baseline and six months]

Change from Baseline Caregiver Stress at 6 months

Assessment of levels of stress:

The Perceived Stress Scale (PSS) is an assessment tool for evaluating stress level. The PSS consists of 10 stress items. Each item represents how often in the last month respondents felt that way from 0 (=never) to 4 (=very often). A total score is the summation of 10 items ranging from 0 to 40. Higher scores indicate higher levels of stress.

[Time Frame: Baseline and six months]

Change from Baseline Reported Positive Aspects of Caregiving at 6 months

Assessment of favorable aspects of caregiving experiences:

An 11-item of Positive Aspect of caregiving (PAC) is an assessment tool for evaluating favorable aspects of caregiving experiences. Each item represents a statement of mental or affective state related to caregiving experiences. Respondents rate to what extent each statement corresponds to their mental or affective state ranging from 0 (=disagree a lot) to 4 (=agree a lot). A total score is the summation of 11 items ranging from 0 to 44. Higher scores indicate higher levels of positive experiences of caregiving.

[Time Frame: Baseline and six months]

Change from Baseline Neuropsychiatric Symptoms in care-recipient/corresponding caregiver distress at 6 months

Presence and severity of neuropsychiatric symptoms and levels of relevant caregiving distress:

Neuropsychiatric Inventory Questionnaire-Q (NPI-Q), a 12-item self-administered questionnaire (NPI-Q), completed by the caregivers about care-recipients for whom they care, is a tool to assess the presence and severity of 12 Neuropsychiatric Symptoms (NPS) in patients with dementia, as well as the caregiver's corresponding distress. Each item asks the presence (1=yes, 0=no), severity (1=mild, 2=moderate, 3=severe), and caregiving distress (0=not at all; 5=extreme or very severe).

[Time Frame: At Baseline]

#### Program Evaluation of GP4C/R4C

Assessment of attitude toward GP4C/R4C system:

A 30-items of USE questionnaire will evaluate participant's attitude toward the GP4C system. The USE questionnaire includes four areas: assess usefulness (8 items), ease of use (11 items), ease of learning (4 items), and satisfaction (7 items). Respondents rate agreement with the statements, ranging from strongly disagree (=1) to strongly agree (=7). Total scores are the summation of items on each area. Higher scores in each indicate a more useful, easier to use, easier to learn, and more satisfied on their experience.

[Time Frame: At six months only]

#### A Composite Psychological Distress Score

A composite score of psychological distress will be constructed. Three measures, depression (CES-D), caregiver stress (PSS), and NPI-Q Distress, will be transformed linearly to have a range from 0 to 100 and then combined with the same weight. This replicates the creation of a dementia burden composite score used in the literature.

## 6 Statistical Methods and Analyses

Caregiver participants will be randomized to the two intervention arms (GP4C and R4C) with the ratio of 1:1. Primary and secondary outcomes, including the Zarit's caregiving burden interview, will be assessed at baseline and 6-month follow-up. Covariates in the analysis include demographic characteristics of the caregivers. Common descriptive statistics (mean, standard deviation, median, interquartile range for continuous variable; frequency and percentage for categorical variables) will be calculated for all covariates in each intervention arm and the two arms will be compared at baseline. Goals of our statistical analysis will be to evaluate the effectiveness of each intervention arm and to compare the two arms. For each intervention arm, the difference between 6-month follow-up and baseline will be computed. Paired t-test and Wilcoxon signed-rank test will be used to detect significant changes in outcome variables at 6-month follow-up since the baseline. Medians, means, and 95% confidence intervals of the differences will be calculated using both empirical percentiles and normal approximation. Multiple comparison adjustments, e.g., Holm-Bonferroni method and Hochberg procedure, will be implemented to control the family wise error rate when testing multiple outcome measures in Section 5.

The two intervention arms will be compared at each follow-up time and for the whole trial period. We will compare the two arms at 6-month follow-up using the two-sample t-test and Wilcoxon rank sum test for each of the two outcomes. The Anderson-Darling test will be used to check the normality assumption at baseline and follow-up times for the two outcome variables. If normal assumption is significantly violated then only nonparametric estimates and tests (i.e., median, IQR, empirical confidence intervals, Wilcoxon signed-rank test, and Wilcoxon rank sum test) will be reported, and data transformation, such as log and square root transformations, will be considered to normalize the outcome variables for further model-based testing. A pre-post analysis will be conducted to model the outcomes at 6-month follow-up to test the intervention arm and covariates adjusting the baseline measurements. The two arms will also be compared incorporating observations from baseline and follow-up in longitudinal analysis of covariance (ANCOVA) models or linear mixed-effects models having the follow-up time and adjusting for covariates.

Given the fact that participants will be randomized into the two arms, the outcome variables will likely be comparable between the two arms at baseline. As a result, the interaction effect between the treatment arm and follow-up time (while adjusting for covariates) will be tested in the longitudinal analysis to evaluate the difference between the two intervention arms because a significant interaction indicates the caregiver's outcome has followed significantly different trajectories in the follow-up period depending on the treatment arm. Missing values may be possible because 1) some caregivers may be lost to follow-up, and 2) some caregiving recipients can be deceased prior to the follow-up. Missing patterns will be inspected and multiple imputation methods, including regression imputation, propensity score imputation, and MCMC imputation will be considered based on the missing mechanism^19. All tests will be two-sided and a p-value less than or equal to 0.05 will be reported as statistically significant. Statistical Analysis Software will be used to conduct the proposed analysis.

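### Per-arm effectiveness is to be judged by within-arm paired tests, which cannot isolate a treatment effect, and nothing ranks the planned between-arm tests above them

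*SAP*

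**What the plan says.** SAP section 6 gives the analysis two aims: "Goals of our statistical analysis will be to evaluate the effectiveness of each intervention arm and to compare the two arms". For the first it computes the six-month minus baseline difference in each arm and says: "Paired t-test and Wilcoxon signed-rank test will be used to detect significant changes in outcome variables at 6-month follow-up since the baseline". The Data Analysis section of the protocol sets the same two goals and the same paired tests.

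SAP section 4.3 and the protocol's sample size section calculate power for a two-sided paired t-test of change from baseline to six months: 80% with 100 caregivers per arm and an effect of 0.28 SD. They conclude that the enrolment "will achieve sufficient statistical power to detect the effectiveness of the proposed interventions".

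The Aim 2 hypothesis in SAP section 2 is comparative: GP4C caregivers "will report greater improvement on primary and secondary outcomes as compared to family caregivers in the R4C condition".

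SAP section 6 also plans comparisons between the arms:
- an unadjusted one: "We will compare the two arms at 6-month follow-up using the two-sample t-test and Wilcoxon rank sum test";
- a baseline-adjusted one: "A pre-post analysis will be conducted to model the outcomes at 6-month follow-up to test the intervention arm and covariates adjusting the baseline measurements";
- a longitudinal one: "the interaction effect between the treatment arm and follow-up time (while adjusting for covariates) will be tested in the longitudinal analysis".

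One significance rule covers everything: "All tests will be two-sided and a p-value less than or equal to 0.05 will be reported as statistically significant". The SAP adds Holm-Bonferroni or Hochberg adjustment across the section 5 outcomes, in the sentence that closes the paragraph on the paired tests. No sentence in either document calls the within-arm tests descriptive or says which analysis decides whether an intervention works.

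**The concern.** Change within one arm is the sum of whatever the intervention does and whatever would have happened anyway: adaptation to the role, regression to the mean, progression of the care recipient's disease, and the effect of being contacted and assessed. Randomisation lets the second part cancel, but only in a contrast between arms. Here both arms receive an online system and contact with a Dementia Care Specialist, and there is no untreated arm. No analysis of this trial can therefore estimate the effectiveness of R4C by itself, and a paired test cannot isolate the effect of GP4C.

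The plan thus offers two routes to a statement that an intervention is effective, and only the between-arm route is valid. A significant paired test could be reported as effectiveness under the plan as written, even if the between-arm difference were null. The per-arm goal is also what the sample size was built on. Recalculating power for the between-arm contrast would not remove the goal or its p-values from the analysis sections.

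**Working it through.** **Inputs.** From SAP section 4.3: 100 completers per arm, effects of 0.28 and 0.33 SD, paired t-test. From SAP section 6: two-sided 0.05, 1:1 allocation. From SAP section 5: eight outcomes defined as change from baseline. Assumed, because the documents do not give it: the natural change in burden, written d, in SDs of the six-month change and positive when favourable.

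**1. Reproducing the plan's figure.** The power of a paired t-test comes from the noncentral t with n − 1 degrees of freedom and noncentrality d√n. At n = 100 and d = 0.28 the noncentrality is 0.28 × 10 = 2.8. Power is 0.792, or 0.7996 by the normal approximation; the plan states 0.800. At d = 0.33 it is 0.9045; the plan states 0.905. All 18 cells of Table 4 reproduce to within one percentage point. A two-sample test at 100 per arm gives 0.504 and 0.641, so the table does describe a within-arm test.

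**2. The same formula with no treatment effect.** If d is purely natural change, the formula gives the chance that an ineffective arm is called significantly improved. The last column is the strictest multiplicity step, Bonferroni over eight outcomes (0.05 / 8 = 0.00625 two-sided).

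| Assumed natural improvement (SD of change) | One ineffective arm significantly improved, unadjusted | Same, strictest step over 8 outcomes |
|---|---|---|
| 0 | 2.5% | 0.3% |
| 0.10 | 17% | 4% |
| 0.20 | 51% | 22% |
| 0.28 | 79% | 51% |

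Under Holm or Hochberg the rate for a given outcome lies between the two columns. A simulation of 20,000 trials gave 17.1%, 50.8% and 79.3% unadjusted at 0.10, 0.20 and 0.28 SD.

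**3. If burden worsens on its own.** At a natural worsening of 0.05 or 0.10 SD the favourable false-positive rate falls to 0.7% or 0.2%. The within-arm error is then of the other kind: a real benefit is offset by the worsening, and the paired test can miss it.

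**4. The between-arm test.** Change shared by the arms cancels. The two-sided error rate is 5%, so 2.5% in favour of GP4C, whatever d is. The simulated two-sided rates were 5.2%, 4.8% and 4.7% at 0.10, 0.20 and 0.28 SD.

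**5. Power of the between-arm test at 100 per arm.** The noncentrality is d√(n/2), where d is now the difference between arms in SDs of change.
- 0.28 SD: 0.28 × √50 = 1.98; power 0.504.
- 0.33 SD: 0.33 × √50 = 2.33; power 0.641.
- Difference detectable with 80% power: about 0.40 SD.

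These figures take no credit for baseline adjustment, because the documents give no baseline to six-month correlation.

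**The case against.** The strongest reply is that the plan already contains what is needed. It specifies three kinds of between-arm analysis, its hypothesis is between-arm, and the goal sentence itself ends with the comparison of the arms. That is correct. A reader might infer that the trial has no valid test of its hypothesis, or that worsening in both arms would conceal a benefit of GP4C from the whole analysis. The documents support neither: the planned contrasts are valid, and shared worsening cancels in them. What remains is that none of them is given priority and the paired tests are not marked as descriptive.

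A second reply concerns size. A reader might infer that the plan would often declare an ineffective arm effective. That depends on natural improvement of roughly 0.10 SD or more, which the documents do not give. They contain hints both ways. The protocol's Significance section says harm becomes more likely the longer care goes on, which suggests worsening. Recruitment of caregivers who are seeking services, or whose relative has just left hospital, could bring people in at a bad moment. Entry criteria set no burden threshold, so regression to the mean is possible but not built in by selection on the score. The rates above are therefore conditional, and with no natural change the paired test has its nominal rate.

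Third, one might suppose that significance in GP4C but not in R4C would be read as superiority. No passage states such a rule; the SAP assigns the difference between arms to the interaction test.

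Fourth, multiplicity adjustment lowers the within-arm rates. It does, but it addresses the number of outcomes and not the confounding with time. At 0.20 SD of natural improvement the strictest step still leaves 22%.

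Finally, a confidence interval that excludes zero conveys the same result as a p-value. This stands as arithmetic, which is why the fix must also say from which contrast effectiveness is concluded.

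**Conclusion.** The concern holds in this form. Both documents make the effectiveness of each arm a goal, pursue it with paired tests and size the trial on one of them. In a trial of two active arms those tests cannot support the conclusion. The valid analyses are present but are not given precedence.

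The size is conditional. Over an assumed natural improvement of 0 to 0.28 SD, an ineffective arm is called significantly improved in 2.5% to 79% of trials unadjusted, or 0.3% to 51% at the strictest adjustment, against a constant 2.5% in favour of GP4C for an unadjusted between-arm test. These figures assume 100 completers per arm and approximately normal changes. This is a defect in what the plan allows to be concluded. It does not make the trial unanalysable, and it should be corrected before results are reported.

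**What to change.** **Analysis text (SAP section 6 and the protocol's Data Analysis section).** Delete per-arm effectiveness as a goal. Report within-arm changes descriptively, as an estimate with a 95% confidence interval and no p-value. State that effectiveness is concluded only from the GP4C minus R4C difference in the baseline-adjusted model of the six-month outcome. That model is already in SAP section 6. The protocol's Data Analysis section does not contain it, so add it there or refer to the SAP.

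**Sample size text (SAP section 4.3 and the protocol's sample size section).** Do not simply reword the conclusion to refer to the between-arm difference: the stated 80% would then be false. Do one of two things:
- label the stated power as that of a within-arm change, and drop the conclusion about detecting effectiveness; or
- restate it for the between-arm contrast: about 50% for 0.28 SD and 64% for 0.33 SD at 100 per arm, with about 0.40 SD detectable at 80% power, before any gain from baseline adjustment.

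**Cost.** The analysis change is wording only and needs no new data or model. Within-arm p-values are no longer reported. If the power is restated, it becomes visibly less favourable.
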